To assess severe, moderate and mild hypoxaemia prevalence among sick children attending intervention primary care facilities, and understand the association of different hypoxaemia cut-offs with adverse outcomes, according to sociodemographic and clinical features.

Implementation and process

- To understand the facilitators and barriers to uptake, acceptability of the intervention and behaviour change by health care providers, caregivers and their children, and a variety of stakeholders at community, health facility, national and international levels
- To evaluate characteristics of children, caregivers, healthcare providers and health facilities associated with uptake and impact of the interventions
- To understand how the interventions affect patient flow and patient-provider interactions, including change in care processes, consultation time, and communication between caregivers and healthcare providers

Cost and cost-effectiveness

- To determine the cost and estimate any cost savings and/or additional costs of introducing pulse oximetry with or without CDAs into primary care in four countries
- To estimate cost effectiveness of the interventions compared to routine care and other interventions aimed at improving the management of severe illness in children 0 – 59 months of age

5 Study design

Health and quality of care impact are evaluated through pragmatic, parallel group, cluster randomised controlled superiority trials in India and Tanzania, and quasi-experimental pre-post studies in Kenya and Senegal.

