- Children 2 – 59 months of age with IMCI signs of moderate / severe disease (IMCI 'yellow' or 'red' classification)

These criteria aim to identify children with the highest likelihood of having hypoxaemia whilst avoid unnecessary referrals of children with a low likelihood of having hypoxaemia and a false positive result, as well as avoiding over-burdening healthcare providers or contributing to clinic delays.

Young infants represent a small proportion of all clinic attendees⁴⁶, but with a relatively high prevalence of hypoxaemia and risk of severe disease and mortality.^{1,7,16} Children with cough or difficulty breathing represent around 40 – 70% of children attending primary care. Children with WHO-defined suspected pneumonia (around 15 – 30% of clinic attendees)^{7,46,47} are more likely to be hypoxaemic than those with cough / cold, but respiratory rate, one of the key differentiating signs is often not measured.^{16,47,48} All children with cough / difficulty breathing are therefore chosen to avoid missing children inappropriately classified as not having suspected pneumonia.

Lastly, children presenting with signs of moderate or severe disease are included to ensure detection of children with illnesses such as sepsis, meningitis, malaria, malnutrition, diarrhoea,

anaemia that may also present with hypoxaemia.^{16,17} Children with mild disease – such as diarrhoea with no evidence of dehydration, fever with no evidence of malaria, meningitis / encephalitis, or complicated measles – are very unlikely to have hypoxaemia and pulse oximetry use will therefore not be advised in this group.

In certain circumstances, there may be a deviation from these criteria for operational reasons. Such circumstances will be agreed with local decision-makers, but, for example, may include the use of pulse oximetry during a triage step in large, high volume facilities. In such circumstances, preference may be given to using pulse oximetry on all sick children. In the event that this occurs, children found to have low oxygen saturation will be triaged for immediate assessment by a clinician, who may repeat the pulse oximetry measurement if needed.

In India, the Ministry of Health and Family Welfare opted to recommend be used in the assessment in all sick children under five years of age.

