8.3.3 Cost and cost-effectiveness study

When all the cost components have been collected, the data will be aggregated or collated in Excel. Once the summary is completed, a cost profile of the programme activities will be derived and after the total costs of the programme have been calculated, the unit costs will then be derived (i.e. total costs divided by the sample size). These profiles are useful in highlighting major cost components (and thus identifying potential areas where improvements in efficiency may have significant impact on costs). For this evaluation, analysis will focus on full costing and incremental costing approach. Total, average and incremental costs per year will be estimated. Costs associated with increasing the oxygen saturation referral threshold will be estimated based on the additional proportion of children meeting referral criteria.

When available, effectiveness data will be combined with the cost data and cost per DALY averted will be estimated. Effectiveness will be modelled using the information on severe outcomes such as mortality, and secondary hospitalization, adjusting as far as possible the level of severity of illness of the child at presentation.

At primary care facilities, these will include measurements (when taken by healthcare providers) such as anthropometry, respiratory rate, temperature and routine investigations where available (e.g. haemoglobin, CRP), and oxygen saturation (post-intervention/in intervention arms). We will also use diagnosis and severity classification recorded by primary care providers.

At hospital level, we will also utilize the same measurement data, and other vital sign data (such as a paediatric early warning score if recorded), decision to admit, intensive care and / or ventilation, provisional and final diagnosis, admission outcome (discharge, death, left against medical advice) and length of hospital stay. We will then use these indicators, along with mortality from phone call follow-up data by Day 28, to predict probability of mortality based on available literature. The DALY calculation will be based primarily on probability of mortality

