4.2 Intervention adherence and Protocol Deviations

While in India pulse oximeter was indicated for all children, in Tanzania, pulse oximeter was indicated for all young infants and for older children with cough/difficult breathing or red/yellow IMCI classification. Cough/difficulty breathing and red/yellow IMCI classification are defined two ways, based on signs and symptoms as reported by the caregiver pre-consultation or on diagnosis made by the healthcare provider during the consultation. These definitions are detailed in a separate document and both will be used, separately, to assess intervention adherence.

Adherence will be evaluated separately for the two intervention arms on the basis of pulse oximeter and CDSA use when indicated.

- ξ Pulse oximetry adherence will be evaluated primarily using information on SpO₂ values from clinical records. Pulse oximetry will be considered used if the RA has found any SpO₂ recording (value readable or unreadable). Pulse oximetry will be considered not used if the RA did not find any recorded SpO₂. Adherence will be additionally evaluated based on pulse oximetry use as reported by the caregivers.
- ξ CDSA adherence will be evaluated by comparing the number of children enrolled and the number of children recorded into the CDSA database. These data will be used to explore further and in more details adherence to the CDSA, but outside the scope of this SAP and it will be detailed in a separate document.

Adherence will be reported overall and weekly by facility.

The following information will be summarised by arm to evaluate deviations to the study protocol:

- ξ Number and percentage of caregivers for which no Day 7 follow-up was attempted.
- ξ Number and percentage of caregivers for which no Day 28 follow-up was attempted.

More general deviations will be recorded by the study team in a study deviation log and categorised into minor and major.

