Antibiotics will be defined in accordance with the WHO antibiotic point prevalence survey (PPS) methodology [7, 8, 9] and therefore only antibacterials for systemic use will be taken into account.

¹ Urgency, as reported by the caregiver, was only collected in Tanzania. For India, urgent referrals will be defined based on the registry alone.

SpO₂ values

SpO₂ should be recorded during the Day0. For the outcomes, the following measures will be taken for spurious and missing SpO₂ values:

- If SpO₂ value is not available, the child will be assumed normoxaemic
- If $70 \leq \text{SpO}_2 < 90\%$, the child will be assumed (with accuracy) to have severe hypoxaemia
- If $40 \leq \text{SpO}_2 < 70\%$, the child will be assumed (with low accuracy) to have severe hypoxaemia
- If $\text{SpO}_2 < 40\%$, the value will be considered spurious (e.g. due to incorrect data entry) and treated as not available, i.e. the child will be assumed normoxaemic.

Additionally, a description of SpO₂ values distribution will be provided based on the following cut-offs:

- $95\% \leq \text{SpO}_2 < 100\%$
- $94\% \leq \text{SpO}_2 < 95\%$
- $92\% \leq \text{SpO}_2 < 94\%$
- $90\% \leq \text{SpO}_2 < 92\%$
- $70\% \leq \text{SpO}_2 < 90\%$ (severe hypoxaemia, accuracy)
- $40\% \leq \text{SpO}_2 < 70\%$ (severe hypoxaemia, but low accuracy)
- Spurious ($0\% \leq \text{SpO}_2 < 40\%$)
- Missing

In India, where three SpO₂ measures were collected, only the first one will be used.

Mild hypoxaemia

$92\% \leq \text{SpO}_2 < 94\%$

Moderate hypoxaemia

$90\% \leq \text{SpO}_2 < 92\%$

Severe hypoxaemia

$\text{SpO}_2 < 90\%$

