6.1.5 Hypoxaemia-related outcomes – only in intervention arms

6.1.5.1 Proportion of children with severe, moderate and mild hypoxaemia, adjusted for sites at high altitude

Hypoxaemic children will be summarised disaggregated by groups based on the following SpO₂ values ranges: SpO₂ < 90%, 90% ≤ SpO₂ < 92% and 92% ≤ SpO₂ < 94%. All children recruited will be in the denominator.

All facilities in India and Tanzania are in low altitude area and therefore no adjustment is required.

6.1.5.2 Proportion of children with hypoxaemia (according to differing cut-offs) with severe complication

Children with severe complication will be summarised disaggregated by groups based on the following SpO₂ values ranges: SpO₂ < 90%, 90% ≤ SpO₂ < 92% and 92% ≤ SpO₂ < 94%. spurious values and missing values. Each SpO₂ group will be the denominator of each proportion.

6.1.5.3 Proportion of children with severe hypoxaemia not meeting any other clinical criteria for severe disease

Children with severe hypoxaemia (according to country's specific cut-off) not meeting any other clinical criteria for severe disease will be counted in the numerator. All children recruited will be in the denominator.

Severe disease will be defined in a separate document.

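### Children in whom oximetry was indicated but who have no usable SpO2 value are scored as having normal oxygen, so hypoxaemia prevalence is understated and moves with measurement coverage

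*SAP*

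**What the plan says.** **The rule.** SAP 6.1.1 (SpO2 values) sets the handling for the outcomes. If the SpO2 "value is not available, the child will be assumed normoxaemic". A value below 40% is deemed spurious and "treated as not available, i.e. the child will be assumed normoxaemic".

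**The denominator.** For severe, moderate and mild hypoxaemia (SAP 6.1.5.1), "All children recruited will be in the denominator". SAP 6.1.5.3, severe hypoxaemia without any other criterion of severe disease, uses the same denominator. Neither outcome has a second denominator.

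**The objective served.** Protocol section 4 lists as an aim "To assess severe, moderate and mild hypoxaemia prevalence among sick children attending intervention primary care facilities".

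**Who was meant to be measured.** SAP 4.2: "While in India pulse oximeter was indicated for all children, in Tanzania, pulse oximeter was indicated for all young infants". Older Tanzanian children qualified through cough or difficult breathing, or through a yellow or red IMCI classification.

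**How the same gap is read for adherence.** SAP 4.2: "Pulse oximetry will be considered not used if the RA did not find any recorded" SpO2. A recording that exists but cannot be read counts as use.

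**What else is planned.** SAP 6.1.1 adds a descriptive SpO2 distribution with separate Spurious and Missing rows. SAP 6.1.5.2 uses each SpO2 group as its own denominator and keeps spurious and missing values apart. SAP 6.3 deals with loss to follow-up, and the sensitivity analyses in SAP 6.2.4 concern the primary outcomes only.

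**The concern.** Prevalence and adherence are separate quantities, and the rule merges them. A child with no recorded SpO2 is a failure to use oximetry in SAP 4.2 and a child with normal oxygen in SAP 6.1.5. A child with an unreadable recording counts as oximetry used in the first section and as normal in the second.

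For indicated children nothing in the documents justifies the assumption. In India no child was exempt, so no absent value can be put down to design. Protocol 8.1.1 also says that register entries in India are often incomplete, which is why trial-specific paper forms are used there. A child may therefore have been measured and found hypoxaemic, yet count as normal because the value was not written down.

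At stake are a stated objective and the estimate of how many severely hypoxaemic children show no other severe sign. Comparability is also at stake: SAP section 6 and SAP 3.7 plan country and pooled results, and the two countries measure under different rules. If coverage differs between arms or countries, the reported prevalence will differ for that reason alone.

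The text also conflicts with itself. SAP 6.1.1 and 6.1.5.1 define severe hypoxaemia as SpO2 below 90% with no lower limit, while SAP 6.1.1 sends values below 40% to normal.

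**Working it through.** The documents give no expected prevalence, coverage or precision for these outcomes, so there is no planned figure to reproduce. Every coverage and prevalence value below is an assumption unless a source is named.

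**Notation.** s = share of recruited children in whom oximetry is indicated; c = share of those with a usable value; p = prevalence among indicated children; q = prevalence among the others, whom I take to be unmeasured.

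- True prevalence = s·p + (1 − s)·q
- Prevalence under the SAP rule, values missing at random among indicated children = s·c·p

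**Step 1: relative error.** With q = 0, SAP/true = c, so the relative shortfall is 1 − c, whatever s and p are.

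| Coverage of indicated children (assumed) | Relative understatement |
|---|---|
| 90% | 10% |
| 80% | 20% |
| 60% | 40% |

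If hypoxaemia is commoner in the unmeasured indicated children than in the measured ones, the shortfall exceeds 1 − c. If it is rarer, the shortfall is smaller. It vanishes only if none of the unmeasured children is hypoxaemic.

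**Step 2: a Tanzanian example.** Take s = 40%, the lower end of the range in Protocol 6.3, where children with cough or difficult breathing "represent around 40 – 70% of children attending primary care". Assume p = 3%, c = 80%, q = 0.

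- True: 0.40 × 3% = 1.2%
- SAP: 0.40 × 0.80 × 3% = 0.96%
- Among measured children only: 3%

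In the planned arm of 36,960 children, 0.40 × 36,960 = 14,784 are indicated. Of these, 0.03 × 14,784 ≈ 444 are hypoxaemic and 0.80 × 444 ≈ 355 are counted. About 89 hypoxaemic children enter as normal.

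With c = 100% and q = 0, the SAP rule gives 1.2%, which is correct. So in Tanzania the error comes from indicated children without a value, not from the all-recruited denominator itself.

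**Step 3: how much rests on q = 0.** With q = 0.3% (assumed), the true figure is 0.40 × 3% + 0.60 × 0.3% = 1.38%. The SAP figure stays at 0.96%, a ratio of 0.70. With c = 100% it is 1.2% against 1.38%, a ratio of 0.87.

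**Step 4: India, s = 100%.** Protocol 3.1 puts hypoxaemia at about 13% of suspected pneumonia, and Protocol 6.3 puts suspected pneumonia at 15–30% of attendees. The product is 0.13 × 15–30% = 1.95–3.9%. These are background figures, used only to set a scale.

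- At 80% coverage: 0.80 × 1.95–3.9% = 1.56–3.12%
- At 60% coverage: 0.60 × 1.95–3.9% = 1.17–2.34%

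**Step 5: comparison between groups.** Take two groups, all children indicated, both with a true prevalence of 3% and with 90% and 60% measured at random. They report 0.90 × 3% = 2.7% and 0.60 × 3% = 1.8%. The ratio of 1.5 comes from measurement alone.

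**The case against.** The strongest defence is that the objective concerns sick children attending intervention facilities, so an all-recruited denominator matches the target. Many Tanzanian children are unmeasured by design, and Protocol 6.3 argues that mild cases are very unlikely to be hypoxaemic. A measured-only figure would overstate prevalence among attendees: 3% against 1.2% in Step 2. This stands, and it limits the point to indicated children.

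Second, part of the remedy is already planned. The Missing and Spurious rows let a reader rebuild a measured-only figure, SAP 6.1.5.2 keeps those groups apart, and SAP 4.2 reports oximetry use when indicated. This stands in part. The plan commits to no measured-only prevalence, and the distribution as specified cannot yield an indicated-only one.

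Third, these are other outcomes of interest in intervention arms only. That stands in full: the comparisons with control are untouched.

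A reader might infer more than the documents support:

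- **That the pilot's 80% threshold is the expected coverage.** Protocol 6.4.1 applies it to providers following the critical steps of oximetry use, not to children with a recorded value.
- **That prevalence in Tanzania could fall from 2% to 0.6–1.1%.** This takes 40–70% with cough × 80% measured = 32–56%, and 2% × 32–56% = 0.64–1.12%. It sets measured children against all attendees. On the same inputs with q = 0, the true attendee figure is 2% × 40–70% = 0.8–1.4%, so the shortfall is 20%. Cough alone also understates the indicated share.
- **That failed readings occur mostly in very sick children.** Nothing in the documents says so, and the point does not need it.

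**Conclusion.** The concern holds for children in whom oximetry was indicated and no usable value exists. For them the plan scores missing data as a normal result, so SAP 6.1.5.1 and 6.1.5.3 understate prevalence whenever such a child is hypoxaemic. If values are missing at random among indicated children and the others are not hypoxaemic, the relative understatement is the unmeasured share: 10%, 20% or 40% at an assumed 90%, 80% or 60% coverage. Actual coverage is not stated, so the size for this trial is unknown.

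Two further conclusions are conditional. Arms or countries would differ artificially only if their coverage differs, and no such difference is documented. A reader might also infer that the cost model is biased, since Protocol 8.3.3 says "Costs associated with increasing the oxygen saturation referral threshold will be estimated based on the additional proportion of children meeting referral criteria". That follows only if the model takes the SAP proportions, and the documents do not say which proportions it uses.

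The primary outcomes do not depend on this rule. The change should be made, but the trial's main conclusions do not rest on it.

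**What to change.** In SAP 6.1.1, 6.1.5.1 and 6.1.5.3:

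1. Treat unavailable and below-40% values as missing for children in whom oximetry was indicated, and reconcile this with the definition of severe hypoxaemia as SpO2 below 90% with no lower limit.
2. Report prevalence among indicated children with a usable value and among all measured children, each with the percentage measured by arm and country. SAP 4.2 has two definitions of the Tanzanian indication criteria (caregiver-reported signs and provider diagnosis), so name the leading one or show both.
3. State that the Tanzanian measured-only figure does not describe all attendees.
4. Keep the all-recruited figure, labelled as a lower bound.

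The cost is a few sentences of SAP text, two extra denominators and slightly longer tables. No new data are needed, because indication and oximetry use are already derived for adherence. SAP 6.1.2.3, 6.1.2.6 and 6.1.5.4 already add restricted denominators to other outcomes.

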Pulse oximeters provide a non-invasive, accurate and easy to use method of evaluating hypoxaemia. A number of observational studies at hospital level have shown significant reductions in child mortality, referrals and triage time following the introduction of pulse oximetry and associated interventions.^{13,25,26} Furthermore, a recent modelling study estimated that implementing pulse oximetry could avert up to 148,000 deaths per year of children under-5 in fifteen high-burden pneumonia countries, far more than the potential deaths averted by IMCI alone.²⁷ In addition to the potential impact on child morbidity and mortality, there are potential resource savings through the reduction in unnecessary oxygen use – up to two thirds of children eligible for oxygen based on WHO criteria are not hypoxic.¹⁴

Whilst most data and guidance relating to pulse oximetry pertains to hospital settings, there is emerging evidence on the benefit in primary care. In Malawi, provision of pulse oximetry to rural health centres and community health workers resulted in increased referral rates among children with WHO-defined severe pneumonia. They also found that pulse oximetry enabled the identification of hypoxaemic children who otherwise would have been categorised as having non-severe pneumonia.¹³ Whilst their study was implemented before the 2014 modification to WHO IMCI guidelines, retrospectively applying the criteria to their dataset revealed that 69% of hypoxaemic children would not have been categorised as requiring referral. Pulse oximetry therefore provides the opportunity to improve the sensitivity of IMCI guidelines for severe disease. Implementation of pulse oximetry could also be a strategy to rule-out severe disease and therefore reduce unnecessary hospital referrals and admissions, though the exact oxygen saturation cut-off requires further validation.²⁸

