Healthcare providers will be advised to use a cut-off of SpO₂ <90% for referral, in line with WHO guidance. The message to refer children with other signs will be reinforced. Different SpO₂ cut-offs for referral for sites at high altitude will be finalised with the IAG and MoHs, given that the normal range for SpO₂ varies with altitude, but this is unlikely to affect cut-offs below 2500m.⁴⁹

Healthcare providers will be advised to only take one measurement for children with severe or moderate disease and will be advised not to attempt to obtain a reading for more than 5 minutes (most readings are obtainable within this time).^{13,50,51} However, if a child with no other sign of moderate or severe disease (i.e. IMCI 'green' category) is found to have SpO₂ <90% (or altitude-specific cut-off), healthcare providers will be advised to repeat the reading. In cases of conflicting readings (i.e. one <90% and one ≥90%, or altitude-specific cut-off), a third reading will be advised as confirmatory.

As the cluster unit is the facility, and more than one level of facility is included in both India and Tanzania, there is a possibility that an intervention lower-level facility (dispensary or PHC) would routinely refer to a non-intervention higher-level facility (health centre or CHC). In this circumstance, a child could be assessed and found to be hypoxaemic with pulse oximetry in a lower-level facility and then be referred to be seen in a facility where pulse oximetry is not routinely being used. To navigate this issue, staff at all lower-level facilities who find a child to be hypoxaemic will be advised that they should refer a child directly to hospital, and only refer to the inpatient / emergency area of a higher-level primary care facility (rather than their outpatient consultation area) if oxygen is available.

The above guidance will be incorporated into the CDSA (facilities in Arm 1) and a paper-based job aid and updated IMCI chartbook (facilities in Arm 2).

Clinical Decision Support Algorithm

In addition to pulse oximetry, healthcare providers in the pulse oximeter plus Clinical Decision Support Algorithm (CDSA) will be guided throughout their medical consultations by an algorithm called ePoct+ and developed by Swiss TPH in collaboration with Unisanté/Wavemind (Lausanne, Switzerland).

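### For India the SAP classifies SpO2 from the first reading only, so an IMCI green child cleared by the protocol's confirmatory reading would count as severely hypoxaemic

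*SAP*

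**What the plan says.** Protocol 6.3 sets out how readings are repeated. Providers are "advised to only take one measurement for children with severe or moderate disease". For a child with no other sign of moderate or severe disease (IMCI green) who reads below 90%, "healthcare providers will be advised to repeat the reading", and if the two readings fall on opposite sides of the cut-off, "a third reading will be advised as confirmatory". The same section says that in India oximetry is to "be used in the assessment in all sick children under five years of age".

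SAP 6.1.1 then says that in India, where three SpO2 "measures were collected, only the first one will be used". It gives no reason. Values from 40% up to 90% are classed as severe hypoxaemia; a missing value, or one below 40%, is treated as normoxaemic.

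The classification feeds the four hypoxaemia outcomes in SAP 6.1.5. In 6.1.5.3, children with severe hypoxaemia "not meeting any other clinical criteria for severe disease will be counted in the numerator". These outcomes serve an objective in Protocol section 4: "To assess severe, moderate and mild hypoxaemia prevalence among sick children attending intervention primary care facilities", together with the association of different cut-offs with adverse outcomes.

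**The concern.** The protocol treats a low first reading in a green child as provisional; the SAP treats it as final. A provider who follows Protocol 6.3 may obtain a normal confirmatory value, yet the analysis would still record severe hypoxaemia.

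The outcome where this bites hardest is 6.1.5.3. Its purpose is not stated in the SAP. The rationale in Protocol 3.1 suggests it: earlier work in Malawi found that oximetry "enabled the identification of hypoxaemic children who otherwise would have been categorised as having non-severe pneumonia". Green children with a false low first reading fall directly into that numerator. Protocol 6.3 itself names false positives in low-likelihood children as a reason for restricting who is measured, and India then extended measurement to all sick children.

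No planned analysis would show the effect. The sensitivity analyses in SAP 6.2.4 concern the primary outcomes only, and the exploratory work on alternative cut-offs varies the threshold, not the reading.

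**Working it through.** **Tracing one child.** A green child in India reads 88%, 96%, 97%.
- Protocol 6.3: first reading low, second conflicts, third confirms a value of 90% or more.
- SAP 6.1.1: first reading 88%, so severe hypoxaemia.

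**Consequence by outcome.**
- 6.1.5.1: the child is added to the below-90% count.
- 6.1.5.2: the child joins the below-90% denominator. If a share *s* of that group is false, the observed risk is (1 − s)R + s·b, where R is the risk in truly hypoxaemic children and b the risk in the others. It is diluted if b < R.
- 6.1.5.3: the child is added to the numerator.
- 6.1.5.4: the main proportion needs hypoxaemia, referral and oxygen at hospital, over all recruited children. A child cleared and not referred changes neither part. Only the additional proportions with hypoxaemic children as denominator change.

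**Illustration of size.** The SAP states no figure to reproduce here. The arm size follows from Protocol 6.6.1:
- per cluster: (110 + 3 × 20)/4 × 12 = 510
- check: 40 × 510 = 20,400, as in the protocol summary
- at the maximum of 60 facilities: N = 60 × 510 = 30,600

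Assumptions not in the documents: all N are measured and green (an upper bound for the counts); true prevalence p below 90% of 0.1% to 1%; false low first reading f of 0.2% to 2%; sensitivity 95% per reading; r is the chance that a repeat is falsely low again (equal to f if errors are independent, otherwise 0.2 or 0.5).

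Formulas:
- true cases, first reading: N·p·0.95
- false cases, first reading: N(1 − p)f
- true cases, protocol sequence: N·p·0.95·[0.95 + 0.05 × 0.95]
- false cases, protocol sequence: N(1 − p)f·[r + (1 − r)r]

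Mid case, p = f = 0.5%:
- first reading: 30,600 × 0.005 × 0.95 = 145 true; 30,600 × 0.995 × 0.005 = 152 false
- protocol sequence: 145 true; the false cases depend on r

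| Rule | True | False | Counted as below 90% | First reading ÷ this rule |
|---|---|---|---|---|
| First reading only | 145 | 152 | 0.97% | – |
| Sequence, independent errors | 145 | 1.5 | 0.48% | 2.03 |
| Sequence, r = 0.2 | 145 | 55 | 0.65% | 1.49 |
| Sequence, r = 0.5 | 145 | 114 | 0.85% | 1.15 |

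Over the whole assumed grid, first-reading false cases run from 61 to 611. With r = 0.5 the sequence still leaves 45 to 459, a reduction of only a quarter, since 1 − (0.5 + 0.5 × 0.5) = 0.25. The smallest inflation is about 5% (p = 1%, f = 0.2%, r = 0.5). The largest ratios, up to about 12, need the rarest true disease, the highest false-low rate and independent errors together (p = 0.1%, f = 2%), and should not be taken as an expectation. At most one true case is lost anywhere on the grid.

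These ratios apply to green children only. Yellow and red children also contribute to 6.1.5.1 and have one reading by design, so the relative change in the overall proportion would usually be smaller.

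**The case against.** The strongest reply is that the SAP does not say what the three Indian measures are. Under Protocol 6.3 most children should have one reading, so three measures could instead be routine triplicates. This stands, and the point is conditional on the sponsor's answer.

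A first-reading rule is also simple and may help comparability with Tanzania in the pooled analysis. That is a fair reason, but the SAP does not give it, and it supports reporting both classifications rather than only one.

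Three stronger inferences are tempting and are not supported:
- **Overall prevalence is overstated.** Missing SpO2 is set to normoxaemic and every recruited child is in the denominator, which pushes the other way. So does scoring a child as normoxaemic when the first value is missing or below 40% but a later one is valid. The net direction cannot be derived.
- **The 6.1.5.3 numerator consists mainly of children due a repeat.** It excludes only severe disease, so yellow children remain in it, and the protocol advises one measurement for them. The documents give no green/yellow split.
- **Providers who followed the rule will look as if they failed to refer.** This can arise only in the additional hypoxaemic-denominator proportions of 6.1.5.4.

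**Conclusion.** The point holds in conditional form. If the three measures are the protocol's repeats, the SAP scores children as severely hypoxaemic whom the trial's own sequence clears, and nothing planned reveals how many. The two passages need to be reconciled.

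The size is unknown. On mid-range assumptions the count among green children is inflated by between about 15% and a doubling, and the benefit of confirmation shrinks as repeat errors become correlated. Every rate used is an assumption. The share of first readings that are false should not be read as the share that confirmation would remove.

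The consequence is bounded. These are other outcomes of interest, reported in intervention arms only, and India has one such arm. Neither primary outcome, the sample size nor the multiplicity procedure uses SpO2. It is a worthwhile, cheap correction and does not threaten the main result.

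**What to change.** First, the sponsor should state what the three Indian measures are. If they are the protocol's repeats, replace the sentence in SAP 6.1.1 with a rule such as:

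- For green children in India with a first valid reading below 90% and a recorded repeat, the below-90% category follows the confirmed result: the second reading if it agrees with the first, or the third if the first two conflict.
- Where confirmation overturns a low first reading, the confirming value sets the mild, moderate or normal band.
- If the readings conflict and no third is recorded, the first reading is kept and the number of such children is reported.
- In all other cases the first valid reading (40% or above) is used, including for the mild and moderate bands, so a missing or below-40% first value does not override a valid later one.

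SAP 4.2 refers to two definitions of red/yellow classification; the rule should name the one used to identify green children.

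Apply this to 6.1.5.1 to 6.1.5.4, and report the first-reading-only classification alongside for the pooled comparison with Tanzania.

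The cost is SAP wording and one derivation on data already collected; clinical practice is untouched. The downside is that the Indian variable is derived differently from the Tanzanian one, which the parallel first-reading report covers.
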